#### 4. STUDY DESIGN

### 4.1. Overall Design

This is a Phase 1, single-arm, open-label, non-randomized, non-controlled, multicenter, study in 6 Chinese adult participants between ages 18 to <75 years with severe hemophilia A or B (defined as Factor VIII (FVIII) or Factor IX (FIX) activity <1%, respectively), with or without inhibitor. This study aims to evaluate the PK, PD, safety and tolerability of a single subcutaneous (SC) dose of PF-06741086.

Approximately 6 participants are planned for enrollment at 2 study sites. Participants who are withdrawn for any reasons may be replaced at the discretion of the investigator and after consultation with the sponsor. Participants will be screened within 35 days prior to administration of the investigational product to confirm that they meet the participant selection criteria for the study. Participants will be admitted into the Clinical Research Unit (CRU) 1 day prior to dosing (Day-1) and will accept a single SC injection of 300 mg PF-06741086 (150 mg \*2) at Day 1. There is no dose modification plan during the study. Participants will be required to stay in the CRU through completion of the Day 7 evaluations. After that, it will be at investigator's discretion on whether the participants should stay in the CRU or not. All participants will return for weekly clinic visits on Day 14, Day 21, and Day 28 per the Schedule of Activities. The follow-up Visit at Day 42 could be a Phone Follow-Up visit or a face to face clinic visit at the discretion of the investigator

Participants who experience a treatment-related adverse event (including lab abnormalitie

s) at any time point will continue to be followed through resolution or stabilization of the event as agreed upon by the investigator and sponsor.

The maximum total duration of the study for a single participant, from initial screening to final follow-up, will be approximately 2.5 months.

CCI

#### 4.2. Scientific Rationale for Study Design

Study B7841010 will be conducted in Chinese adult participants 18 to <75 years of age with severe hemophilia A or B, with or without inhibitor. This population also matches the entry criteria for the global pivotal Phase 3 study. The mechanism of action of PF-06741086 through the extrinsic cascade predicts it would be effective in both forms of hemophilia. Similarly, it is acceptable to enroll both those with inhibitors and those without, because the mechanism of action is not expected to be influenced by the presence of inhibitors to either FVIII or FIX. The clinical risk/benefit profile for this population is considered appropriate for the evaluation of PK, PD, safety and tolerability of PF-06741086.

The primary objective of Study B7841010 is to evaluate the safety and tolerability of a single SC dose of PF-06741086. Secondary objectives include evaluating the PK, PD properties and immunogenicity of PF-06741086. Selection of the PD endpoints and sampling schedule are based on results from non-clinical studies, the Phase 1 FIH study and Phase 1b/2 first-in patient (FIP) study results. They will reflect either target binding by PF-06741086 (ie, TFPI [total and free] levels) or downstream pharmacologic effects of TFPI inhibition (ie, dPT, TGA, PF1+2 and D-dimer). Thrombosis is a potential risk for inhibition of TFPI, and PF-06741086 is expected to significantly inhibit TFPI, particularly at the highest dose levels. To minimize this risk, hemophilia patients with a known history of thrombotic, ischemic or coronary artery disease, or known pro-thrombotic conditions (eg, Protein C deficiency) will be excluded from this study. Safety monitoring will include laboratory parameters that may be modulated due to coagulopathy (eg, [PT]/INR, APTT, fibrinogen, ATIII and platelet counts) and parameters to screen for possible thrombotic events (eg, cardiac troponin I). Laboratory endpoints to detect excessive modulation of the coagulation pathway will be monitored during the period of peak drug exposure, until at least 28 days have passed since the investigational drug administration.

Potential risks for treatment with PF-06741086 are thrombi or emboli. Depending on location and severity, thrombi or emboli may be life threatening or fatal. An additional potential risk for treatment with PF-06741086 is ADA-induced hypersensitivity. Additional safety information for PF-06741086 is available in the IB.

Demonstration of PK, PD, safety and tolerability profile that is supportive for chronic treatment on an acceptable dosing schedule will permit progression to subsequent investigations in Chinese patients with severe hemophilia.

[figure not shown]
#### 4.3. Justification for Dose

The purpose of this study is to characterize the PK, PD, safety and tolerability profiles following a single SC dose of 300 mg PF-06741086 in Chinese adult participants with severe hemophilia A or B, with or without inhibitor.

The dose justification for this study is based on considerations outlined below.

Phase 1 FIH study B7841001 and Phase 1b/2 FIP study B7841002.

All doses administered in this study were well tolerated and there were no SAEs, severe TEAEs, or safety laboratory values of concern for these participants. There were also no reported infusion or injection site reactions. The PK parameters could not be characterized after the 30-mg dose administration,

# 4.3.2. Dose justification of a single dose of 300 mg PF-06741086 SC in this study

A single 300 mg PF-06741086 SC proposed in this study

- the dose administered to a cohort of 6 Western and a cohort of 4 Japanese subjects in B7841001 so that the intensive Chinese PK data, can be compared with that from the Western group in B7841001.
- the first dose administered to non-inhibitor subjects in Cohort 1 (300 mg QW) and Cohort 2 (a 300 mg loading dose, followed by 150 mg QW), and to inhibitor subjects in Cohort 4 (300 mg QW) of B7841002.

Based on the above justification, a single dose of 300 mg PF-06741086 SC is proposed for this China standalone study, CCI

#### 4.4. End of Study Definition

A participant is considered to have completed the study if he has completed all phases of the study including the last scheduled procedure shown in the schedule of activities.

The end of the study is defined as the date of the last visit of the last participant in the study or last scheduled procedure shown in the schedule of activities for the last participant in the trial globally.

#### 5. STUDY POPULATION

This study can fulfill its objectives only if appropriate participants are enrolled. The following eligibility criteria are designed to select participants for whom participation in the study is considered appropriate. All relevant medical and nonmedical conditions should be taken into consideration when deciding whether a particular participant is suitable for this protocol.

Prospective approval of protocol deviations to recruitment and enrollment criteria, also known as protocol waivers or exemptions, is not permitted.

#### 5.1. Inclusion Criteria

Participants are eligible to be included in the study only if all of the following criteria apply:

## Age, Sex and Weight:

1. Participant must be male and 18 to <75 years of age with a minimum body weight of 30 kg at the time of signing the informed consent.

## Type of Participant and Disease Characteristics:

- 2. Participants with a diagnosis of severe hemophilia A or B (FVIII or FIX activity <1%, respectively).
- 3. Participants without inhibitor must also meet the following criteria:
  - No detectable or documented history of inhibitors (≥0.6 BU/mL or greater than the upper limit of normal [ULN] for the testing laboratory) against FVIII or FIX prior to enrollment.
  - Participants with on-demand treatment regimen with ≥6 acute bleeding episodes (spontaneous and/or traumatic) that required coagulation factor infusion during the 4 months period prior to Screening and willing to continue to receive on-demand treatment during the study. Surgical bleeding episodes do not apply to this criterion.
- 4. Participants with inhibitor must also meet the following criteria:

- Documentation of current high titer inhibitor (≥5 BU/mL) or current low titer inhibitor (<5 BU/mL) refractory to FVIII or FIX replacement and with FVIII or FIX recovery <60% of expected within previous 4 months prior to screening.
- Participants with on-demand treatment regimen with ≥6 bleeding episodes (spontaneous and/or traumatic) necessitating treatment with bypass factor for at least 4 months prior to screening and willing to continue to receive on-demand treatment during the study. Surgical bleeding episodes do not apply to this criterion.

#### **Informed Consent:**

5. Capable of giving signed informed consent as described in Appendix 1, which includes compliance with the requirements and restrictions listed in the informed consent document (ICD) and in this protocol.

#### 5.2. Exclusion Criteria

Participants are excluded from the study if any of the following criteria apply:

#### **Medical Conditions:**

- 1. Previous or current treatment for and/or history of coronary artery diseases, venous or arterial thrombosis (Common Terminology Criteria for Adverse Events [CTCAE] Grade >1), or ischemic disease (except treatment for catheter-associated thrombosis).
- 2. Known planned surgical procedure during the planned study period.
- 3. Known hemostatic defect other than hemophilia A or B.
- 4. Abnormal renal or hepatic function as defined by the following laboratory results at Screening:
  - a. Alanine transaminase (ALT)  $>2 \times$  upper limit of normal (ULN).
  - b. Bilirubin  $>1.5 \times ULN$  (isolated bilirubin  $>1.5 \times ULN$  is acceptable if bilirubin is fractionated and direct bilirubin <35%).
  - c. Current unstable liver or biliary disease per investigator assessment defined by the presence of ascites, encephalopathy, coagulopathy, hypoalbuminaemia, oesophageal or gastric varices, persistent jaundice, or cirrhosis. NOTE: Stable chronic liver disease (including Gilbert's syndrome, asymptomatic gallstones, and chronic stable hepatitis B or C -eg, presence of hepatitis B surface antigen [HbsAg] or positive hepatitis C antibody test result at screening or within 3 months prior to starting study intervention) is acceptable if the participant otherwise meets entry criteria.
  - d. Serum albumin less than the lower limit of normal (LLN).
  - e. Estimated glomerular filtration rate (eGFR) <30 mL/min/1.73 m^2.
- 5. Abnormal hematology values as defined by the following laboratory tests at Screening:
  - a. Platelet count <100,000/U1
  - b. Fibrinogen level <LLN
  - c. Hemoglobin level <10 g/Dl

- 6. Abnormal coagulation activity as defined by the following laboratory results at Screening:
  - a. Prothrombin time (PT)  $> 1.25 \times ULN$ .
- 7. Other acute or chronic medical or psychiatric condition including recent (within the past year) or active suicidal ideation or behavior or laboratory abnormality that may increase the risk associated with study participation or investigational product administration or may interfere with the interpretation of study results and, in the judgment of the investigator, would make the participant inappropriate for entry into this study.
- 8. Corrected QT interval (QTc) >450 msec for male participants or QTc >480 msec in participants with bundle branch block.
- 9. Individuals with hypersensitivity or an allergic reaction to hamster protein or other components of the study intervention.
- 10. A positive urine drug screen.

# **Prior/Concomitant Therapy:**

- 11. Current routine prophylaxis with bypassing agent (eg, activated prothrombin complex concentrate (aPCC), Prothrombin Complex Concentrates [PCC], and/or rFVIIa) or non coagulation factor-replacement therapy (eg, emicizumab).
- 12. Regular, concomitant therapy with immunomodulatory drugs (eg, IV immunoglobulin [IVIG], and routine systemic corticosteroids, rituximab).
- 13. Ongoing or planned use of immune tolerance induction during the study phase, or prophylaxis with FVIII or FIX replacement during the study.

# **Prior/Concurrent Clinical Study Experience:**

14. Participation in other studies involving investigational drug(s) within 30 days (or as determined by local requirements) or 5 half-lives prior to study entry and/or during study participation.

#### **Diagnostic Assessments:**

- 15. CD4 cell count ≤200/Ul if human immunodeficiency virus (HIV)-positive
- 16. Baseline 12-lead ECG that demonstrates clinically relevant abnormalities that may affect participant safety or interpretation of study results.

#### **Other Exclusions:**

17. Investigator site staff members directly involved in the conduct of the study and their family members, site staff members otherwise supervised by the investigator, or Pfizer employees, including their family members, directly involved in the conduct of the study.

#### 5.3. Lifestyle Considerations

No lifestyle restrictions are required.

#### 5.4. Screen Failures

Screen failures are defined as participants who consent to participate in the clinical study but are not subsequently entered in the study. A minimal set of screen failure information is required to ensure transparent reporting of screen failure participants to meet the Consolidated Standards of Reporting Trials (CONSORT) publishing requirements and to respond to queries from regulatory authorities. Minimal information includes demography, screen failure details, eligibility criteria, and any serious adverse event (SAE).

Screen failure data are collected and remain as source and are not reported to the clinical database.

Individuals who do not meet the criteria for participation in this study (screen failure) may be rescreened. Rescreened participants should be assigned the same participant number as for the initial screening.

#### 6. STUDY INTERVENTION

Study intervention is defined as any investigational intervention(s), marketed product(s), placebo, or medical device(s) intended to be administered to a study participant according to the study protocol.

For the purposes of this protocol, the term investigational product may be used synonymously with study intervention.

## 6.1. Study Intervention(s) Administered

ARM Name	PF-06741086		
Intervention Name	PF-06741086		
Type	Biological product		
Dosage Form	Injectable		
CCI			
Dosage	300 mg once a		
Route of Administration	Subcutaneous injection Subcutaneous injection		
IMP and NIMP c	IMP		
Sourcing	Provided centrally by the sponsor		
Packaging and Labeling	Study Intervention will be provided in a sterile liquid solution for injection packaged in a prefilled syringe for single use. Each package will be labeled as required per country requirement.		

b. Following an overnight fast of least 10 hours, participants will receive PF-06741086 by SC injection at approximately 0800 hours (plus or minus 2 hours). All participants will be required to refrain from lying down (except when required for blood pressure, pulse rate, and ECG measurements), eating, and drinking beverages other than water during the first 4 hours

after dosing. The number of injections and injection sites will be recorded. The preferred body locations of the SC injections are the front of the middle thigh, including anterolateral, or outer area of the upper arm. If an arm is used for the SC injection, the opposite arm should be used for the PK/PD blood sample collections, if possible.

c IMP= investigational medicinal product; NIMP= non-investigational medicinal product

## 6.1.1. Medical Devices

- 1. Instructions for medical device use as a prefilled syringe are provided in the Investigational Product Manual.
- 2. Prefilled syringe medical device incidents, including those resulting from malfunctions of the device, must be detected, documented, and reported by the investigator throughout the study (see Section 8.3.8).

# 6.2. Preparation/Handling/Storage/Accountability

- The investigator or designee must confirm appropriate temperature conditions have been maintained during transit for all study interventions received and any discrepancies are reported and resolved before use of the study intervention, as applicable for temperature monitored shipments.
- 2. Only participants enrolled in the study may receive study intervention and only authorized site staff may supply or administer study intervention. All study interventions must be stored in a secure, environmentally controlled, and monitored (manual or automated recording) area in accordance with the labeled storage conditions with access limited to the investigator and authorized site staff. At a minimum, daily minimum and maximum temperatures for all site storage locations must be documented and available upon request. Data for nonworking days must indicate the minimum and maximum temperature since previously documented for all site storage locations upon return to business.
- 3. The investigator, institution, or the head of the medical institution (where applicable) is responsible for study intervention accountability, reconciliation, and record maintenance (ie, receipt, reconciliation, and final disposition records). All study interventions will be accounted for using an investigational product accountability form/record.
- 4. Further guidance and information for the final disposition of unused study interventions are provided in the IP manual.
- 5. Any storage conditions stated in the SRSD will be superseded by the storage conditions stated on the product label.
- Study interventions should be stored in their original containers and in accordance with the labels.

- 7. See the investigational product manual (IP manual) for storage conditions of the study intervention once reconstituted and/or diluted.
- 8. Any excursions from the study intervention label storage conditions should be reported to Pfizer upon discovery along with any actions taken. The site should actively pursue options for returning the study intervention to the storage conditions described in the labeling, as soon as possible. Once an excursion is identified, the study intervention must be quarantined and not used until Pfizer provides permission to use the study intervention. It will not be considered a protocol deviation if Pfizer approves the use of the study intervention after the temperature excursion. Use of the study intervention prior to Pfizer approval will be considered a protocol deviation. Specific details regarding the definition of an excursion and information the site should report for each excursion will be provided to the site in the IP manual.
- 9. The sponsor or designee will provide guidance on the destruction of unused study intervention (eg, at the site). If destruction is authorized to take place at the investigator site, the investigator must ensure that the materials are destroyed in compliance with applicable environmental regulations, institutional policy, and any special instructions provided by Pfizer, and all destruction must be adequately documented.

## 6.2.1. Preparation and Dispensing

See the investigational product manual (IP manual) for instructions on how to prepare the investigational product for administration. Investigational product should be prepared and dispensed by an appropriately qualified and experienced member of the study staff (eg, physician, nurse, physician's assistant, nurse practitioner, pharmacy assistant/technician, or pharmacist) as allowed by local, state, and institutional guidance.

#### **6.2.2.** Allocation to Investigational Product

This is an open-label, single-arm study. The investigator's knowledge of the treatment should not influence the decision to enroll a particular participant or affect the order in which participants are enrolled.

The investigator will assign participant identification numbers sequentially to the participants as they are screened for the study. This identifying number will be retained throughout the study. A participant identifying number must never be reassigned or reused for any reason.

Study intervention will be dispensed at the study visits summarized in the Schedule of Activities (SoA).

Returned study intervention must not be redispensed to the participants.

#### **6.3. Study Intervention Compliance**

Participant compliance with investigational product will be assessed.

Compliance will be assessed by direct questioning. Deviation(s) from the prescribed dosage regimen should be recorded in the case report form (CRF).

All doses of investigational product will be administered by the appropriately designated study staff at the investigator site.

## **6.4.** Concomitant Therapy

Participants will abstain from all prohibited concomitant medications, except for the treatment of adverse events or acute bleeding episodes as described in Section 6.4.1 of this protocol. All concomitant treatments taken during the study must be recorded with indication, and start and stop dates of administration. All participants will be questioned about concomitant treatments at each clinic visit. If a participant receives a prohibited concomitant medication during their participation in the study, the participant's continued participation in the study will be decided on a case-by-case basis, at the discretion of the investigator and sponsor.

For emergency or unplanned surgical interventions, investigators must contact the sponsor's medical monitor as soon as possible to review concomitant treatments and any impact on participant participation.

Treatments taken within 28 days prior to informed consent being signed will be documented as a prior treatment. Treatments taken from date of signed informed consent will be documented as concomitant treatments.

#### 6.4.1. Prohibited Medications

Factor VIII (within 72 hours) or Factor IX replacement therapy (within 96 hours), extended half-life FVIII or FIX replacement therapy (within 4 x half-life) or bypass agent therapy (rFVIIa, PCC or aPCC: within 72 hours) before Screening is prohibited. Depending on the coagulation factor product in use, additional wash out time may be required prior to the screening assessments to achieve a factor activity level  $\leq 1\%$ . If a participant experiences an acute bleeding episode during this washout period requiring treatment with a Factor VIII or IX replacement therapy, or bypass agent therapy, the participant is to be stabilized utilizing this regimen and a new washout period should be initiated. The regimen used to treat the episode should be recorded as a prior medication.

Factor VIII (within 72 hours) or Factor IX replacement therapy (within 96 hours), extended half-life FVIII or FIX replacement therapy (within 4 x half-life) or bypass agent therapy (for rFVIIa, PCC or aPCC: at least 72 hours) before Day 1 treatment is also prohibited. If a participant experiences an acute bleeding episode during this washout period requiring treatment with a Factor VIII or IX replacement therapy, or bypass agent therapy the participant is to be stabilized utilizing this regimen and a new washout period should be initiated. The regimen used to treat the episode should be recorded as a concomitant medication. All acute bleeding episodes between Screening and Day 1 must be recorded. Treatment with **rFVIIa at a dose level greater than approximately 90 µg/kg and to exceed a dosing frequency of approximately every 2 hours is prohibited throughout the study**. If a participant receiving investigational product is subsequently administered a rFVIIa dose greater than approximately 90 µg/kg or more frequent than every 2 hours, the investigator must immediately contact the

sponsor's medical monitor to discuss the case to determine if the respective participant should continue to receive IP, remain in the study, or be withdrawn immediately.

The following are prohibited throughout the study: immunomodulatory medications (eg, IVIG, routine systemic corticosteroids, rituximab), emicizumab, aPCC. Bypassing agent therapy is not permitted at any time for participant without inhibitor.

The use of antifibrinolytic agents or medications known to influence platelet function (eg, aspirin, certain non-steroidal anti-inflammatory drugs (NSAIDs) or certain traditional Chinese medicines (TCMs)) within 5 days before initial study drug administration through Day 42 is prohibited.

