# **6.4.2.** Treatment(s) for Bleeding Episodes

Bleeding episodes that occur during this study may be treated (on-demand) with hemostatic therapy (recommend intravenous factor products for participants without inhibitors; rFVIIa bypass agent therapy at approximately 90 µg/kg and not to exceed a dosing frequency of every 2 hours for participants with inhibitors; or PCC at the lowest effective dose, in accordance with the Product Prescribing Information) as deemed appropriate by the investigator. The specific treatment with hemostatic therapy is at the discretion of the subject/caregiver/investigator, but all doses of hemostatic therapy taken after signing of informed consent will be documented as concomitant medications or concomitant treatments.

If a participant experiences a bleeding episode during the washout period preceding screening laboratory assessments, the participant is to be stabilized utilizing the participant's usual hemostatic treatment regimen. Once the bleeding episode has been successfully treated a new washout period should be completed prior to obtaining the screening laboratory tests.

If a participant experiences a bleeding episode during the washout period preceding the initial administration of PF-06741086 the participant is to be stabilized utilizing the participant's usual hemostatic treatment regimen and a new washout period should be implemented. Once treatment of the bleeding episode with hemostatic agents has been completed a new washout period should be initiated in anticipation of the initial treatment with PF-06741086.

If a participant experiences a bleeding episode during the PK assessment period following administration of PF-06741086, the participant is to be stabilized utilizing the Factor VIII or Factor IX treatment regimen at the lowest effective dose according to the approved Product Prescribing Information, or rFVIIa bypass agent therapy at approximately 90  $\mu$ g/kg and not to exceed a dosing frequency of every 2 hours, or PCC at the lowest effective dose, in accordance with the Product Prescribing Information, and protocol specified observations and procedures should proceed to completion.

If a participant experiences a bleeding episode after Day 28 following the initial administration of PF-06741086, the participant is to be stabilized utilizing the participant's usual hemostatic treatment regimen.

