Treatment with aPCC or other plasma product (eg: Fresh frozen plasma or cyoprecipitate) in accordance with approved product labeling may be allowed only in the following scenarios in cases where such treatment is considered medically necessary during an emergency situation:

- rFVIIa provides insufficient control of participant's bleeding;
- in the absence of suitable hemostatic medication.

The use of hemostatic medications for bleeding episodes as specifically outlined in this Section (6.4.2) is not considered to be a protocol violation.

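### Protocol 6.4.1 and 6.4.2 do not agree on when exceeding an rFVIIa limit is prohibited, or on which rFVIIa and aPCC rules apply to bleeds after Day 28

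*Protocol*

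**What the plan says.** Four parts of the protocol bear on this.

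- **The prohibition (6.4.1, bold).** rFVIIa at a dose above about 90 µg/kg "and to exceed a dosing frequency of approximately every 2 hours is prohibited throughout the study".
- **The contact trigger (6.4.1, next sentence).** For a participant who has had study drug and then receives an "rFVIIa dose greater than approximately 90 µg/kg or more frequent than every 2 hours, the investigator must immediately contact" the medical monitor, to decide on continuation or withdrawal.
- **The aPCC ban (6.4.1).** "The following are prohibited throughout the study: immunomodulatory medications", in a list that also names emicizumab and aPCC. The same paragraph bars bypassing agents at any time for participants without inhibitor.
- **Bleed treatment (6.4.2).** The opening paragraph covers bleeds during the study and recommends "rFVIIa bypass agent therapy at approximately 90 µg/kg and not to exceed a dosing frequency of every 2 hours for participants with inhibitors". It adds: "The specific treatment with hemostatic therapy is at the discretion of the subject/caregiver/investigator". The paragraph on the PK assessment period repeats both rFVIIa limits. The next paragraph deals with a "bleeding episode after Day 28 following the initial administration of PF-06741086, the participant is to be stabilized utilizing the participant's usual hemostatic treatment regimen". The section then allows aPCC only in two emergency situations, and closes by stating that haemostatic use "as specifically outlined in this Section (6.4.2) is not considered to be a protocol violation".

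Section 6.4 makes the label matter. If a participant receives a prohibited medication, continued participation is decided case by case by the investigator and sponsor. Follow-up runs to Day 42 (4.1), and so does the primary adverse-event endpoint (Section 3; SAP 3.1).

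**The concern.** There are two separate problems.

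First, a site treating a bleed in a participant with inhibitor cannot tell from 6.4.1 whether exceeding one rFVIIa limit alone is a prohibited treatment. It must call the medical monitor, but the sentence that defines the prohibition does not cover the case.

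Second, for Days 29 to 42 one section keeps the rFVIIa limit and the aPCC ban in force, while the other directs the usual regimen and declares treatment under that section not to be a violation. A participant whose usual regimen lies outside the limits falls under both.

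At stake are consistent conduct across the two sites and consistent classification of deviations in a study whose primary objective is safety. Thrombosis is a stated potential risk that may be life-threatening or fatal (2.3, 4.2), and possible additive effects with rFVIIa were examined in rats (2.2.1).

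**Working it through.** The plan gives no figure to reproduce, so the check compares the texts and counts days.

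**1. Logic of the two limits.** Inputs: the prohibition and the contact trigger in 6.4.1, and the regimen in 6.4.2.

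| Dose above about 90 µg/kg | More often than every 2 h | Literal ban (6.4.1) | Contact trigger (6.4.1) | Within the 6.4.2 regimen |
|---|---|---|---|---|
| No | No | No | No | Yes |
| Yes | No | No | Yes | No |
| No | Yes | No | Yes | No |
| Yes | Yes | Yes | Yes | No |

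The ban covers 1 of 4 combinations and the trigger 3 of 4, so they differ on 3 − 1 = 2. In those two rows the treatment calls for urgent escalation and lies outside the described regimen, yet is not literally prohibited. The opening of 6.4.2 does not settle this, because the regimen there is a recommendation and the choice is left to the participant, caregiver or investigator. Nor does 6.4, which excepts treatment of acute bleeds from the prohibited list but refers the reader to 6.4.1, where the ban itself stands.

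**2. Period of conflict.** Days 29 to 42 are 42 − 28 = 14 days, and 14/42 = 33% of the primary adverse-event window. With the ±7-day window on the last visit, the study can run to Day 42 + 7 = Day 49.

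| Agent | 6.4.1 | 6.4.2, after Day 28 | 6.4.2, other text without an end date |
|---|---|---|---|
| rFVIIa | Limited for the whole study; contact trigger has no end date | Usual regimen, no limit repeated | Opening recommendation, about 90 µg/kg and every 2 h |
| aPCC | Banned for the whole study | Usual regimen, aPCC not mentioned | Emergency use only |

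aPCC therefore has three statements that do not agree. For rFVIIa, the study-long limit and the post-Day-28 sentence do not agree, and the closing statement on violations does not say which governs.

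**3. Drug remaining at Day 28.** Day 28 is 27 days after dosing: 27 × 24 = 648 h. Section 2.2.3.2.1 quotes half-lives from 33.3 h (mean, 100 mg SC) to 122 h (one Japanese participant at 300 mg SC).

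- 648/33.3 = 19.5 half-lives
- 648/122 = 5.3 half-lives

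The short value is not for the 300 mg dose, so the long one is the cautious choice. Counted from the latest quoted SC peak time (108 h), it gives (648 − 108)/122 = 4.4 half-lives, or 0.5^4.4 ≈ 5% of the peak, assuming log-linear decline.

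**4. Who is affected.** Because 6.4.1 bars bypassing agents without inhibitor, both conflicts concern participants with inhibitor. The first arises only if rFVIIa exceeds exactly one limit. The second arises only if the usual regimen lies outside the limits or is aPCC. The protocol fixes no number with inhibitor among the approximately 6 planned, so the number affected could be zero.

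**The case against.** The strongest reply is that this is untidy drafting. A prohibition and a notification trigger do different jobs, a trigger wider than the ban is coherent, and obeying one never breaches the other. The conjunction may be a slip, since the PK-period paragraph of 6.4.2 states both limits. Participants are confined through the Day 7 evaluations (4.1), which spans the quoted peak times of 48 to 108 h. All haemostatic doses are recorded as concomitant treatment (6.4.2) and listed (SAP 6.5.8), and bleeds are summarised for Days 1 to 42 (SAP 6.5.4). With about 6 participants the exposures can be traced.

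Much of this stands. The two sentences in 6.4.1 are not contradictory in strict logic, and the exposure data are not lost. The reply does not establish whether exceeding one limit is a prohibited treatment, or which section governs Days 29 to 42.

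Four stronger readings are tempting, but the documents do not support them.

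- **That no limit applies after Day 28.** The silence is in one sentence. The study-long wording of 6.4.1, the opening of 6.4.2 and the emergency-only rule for aPCC still nominally cover those days.
- **That one site would call the medical monitor and another would not.** For rFVIIa the trigger applies if either limit is exceeded and has no end date, so any excess after study drug requires the call.
- **That these limits are the main control on thrombosis.** Section 4.2 names exclusion of at-risk participants and laboratory monitoring. The protocol gives no reason for the rFVIIa limit.
- **That the entry criterion of at least six bleeds yields an expected number of affected bleeds.** It is a pre-dose minimum, not an on-study rate, and most of the conflict cannot reach participants without inhibitor.

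**Conclusion.** The point holds as a conflict of wording in a bolded safety restriction. The literal ban and the contact trigger differ on 2 of 4 combinations of the rFVIIa limits, and the status of exceeding one limit alone is undefined whenever such a bleed is treated. For the last 14 of 42 days, the study-long rFVIIa limit and aPCC ban conflict with the direction to use the usual regimen, and for aPCC a third, emergency-only rule is added.

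The size is modest. Only participants with inhibitor are reached, in a number the documents do not give. After Day 28 the issue is mainly one of rule and deviation recording, on the assumption that the half-lives quoted from the first-in-human study carry over to this population. No sample size, estimate or planned analysis changes. Which clinical rule is right is not judged here.

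**What to change.** Reconcile 6.4.1 and 6.4.2.

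- Use the same logic for the dose and frequency limits in the prohibition, the contact trigger and the bleed-treatment text, so that it is clear whether exceeding one limit is prohibited.
- Give the rFVIIa limit and the aPCC restriction each one stated period and one stated set of exceptions, and make the post-Day-28 sentence and the closing statement on violations agree with them.
- Correct the cross-reference in 6.4 so that the exception for acute bleeds points to the text that describes their treatment.

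The sponsor's clinicians should decide which rule stands. The cost is wording in adjacent sections and a memo to the two sites, with no extra procedures or participants.
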